**Table 14-6 Overall response at each assessment**

Measurable response Target and new measurable lesions (Tumor burden), * (%)	Non-measurable response Non-target lesions (both baseline and new non-measurable)	Overall response Using irRC
- 100	Absent	irCR a
- 100	Stable/not evaluated	irPR a
≤-30	Absent/Stable/not evaluated	irPR a
>-30 and <+20	Absent/Stable/not evaluated	irSD

---

≥+20	Any	irPD a
Any	Unequivocal progression	irPD a

---

\*the diameter of new measurable lesions is included in the calculation of the sum of diameters.

a To be confirmed after at least 4 weeks.

---

If the evaluation of any of the target lesions could not be made during follow-up, the overall status must be ‘unknown’ unless progression was documented.

If the evaluation of any non-target lesions is not made, and all target lesions disappeared, irCR cannot be determined and overall response must be “irPR”.

In some circumstances it may be difficult to distinguish residual disease from normal tissue. When the evaluation of complete response depends on this determination, it is recommended that the residual lesion be investigated (fine needle aspirate/biopsy) to confirm the irCR.

#### **14.2.5 Only non-measurable disease at baseline**

For patients with only non-measurable disease at baseline, unequivocal progression of non-target lesions will constitute an irPD (i.e. worsening of the overall tumor burden which is substantial enough to lead to discontinuation or change of therapy). In addition, the appearance of new lesions (measurable or non-measurable) consistent with unequivocal progression taking into account the overall disease burden will constitute an irPD. The absence of all non-target lesions and no new lesions will qualify for irCR. Otherwise the overall response will be considered as irNon-CR/Non-PD (irNCRNPD) similar to RECIST 1.1. Confirmation of irPD and irCR as specified above in (Section 14.2.4) is required. If any baseline non-target lesion or a new lesion observed at an earlier post-baseline evaluation was not/could not be assessed at a later post-baseline tumor evaluation then the overall response will be irUNK. No confirmation is required for irNCRNPD.

## 14.3 Appendix 3: Statistical details of Phase I Bayesian logistic regression models (BLRM) and Phase II hierarchical models

### 14.3.1 Phase I BLRM

An adaptive Bayesian logistic regression model (BLRM) guided by the escalation with overdose control (EWOC) principle will be used to make dose recommendations and estimate the maximum tolerated dose (MTD) and/or identify the recommended dose for Phase II (RP2D) during the dose escalation part of the study. The use of Bayesian response adaptive models for Phase I studies has been advocated by the [EMA guideline on small populations \(2006\)](#) and by [Rogatko \(2007\)](#) and is one of the key elements of the FDA's Critical Path Initiative.

In the single-agent LAG525 dose escalation part, the dose-toxicity (DLT) relationship is described by the following 2-parameter BLRM:

$$\text{logit}(\pi_1(d_1)) = \log(\alpha_1) + \beta_1 \log(d_1/d_1^*), \quad \alpha_1 > 0, \beta_1 > 0$$

where  $\text{logit}(\pi_1(d_1)) = \log(\pi_1(d_1)/(1-\pi_1(d_1)))$ , and  $\pi_1(d_1)$  is the probability of a DLT at dose  $d_1$ , where  $d_1$  represents the Q2W dose of LAG525. Doses are rescaled as  $d_1/d_1^*$  with reference dose  $d_1^* = 3$  mg/kg of LAG525. As a consequence  $\alpha_1$  is equal to the odds of DLT rate at  $d_1^*$ . Note that for a dose equal to zero, the probability of toxicity is zero.

In the dose escalation for the combinations, the dose-toxicity (DLT) relationship is modeled by a 5-parameter BLRM as follows. Let  $\pi_1(d_1)$  be the probability of DLT if LAG525 is given as a single agent at Q2W dose  $d_1$ , and  $\pi_2(d_2)$  the probability of DLT if PDR001 is given as a single agent at Q2W dose of  $d_2$ .  $\pi_{12}(d_1, d_2)$  denotes the probability of DLT if LAG525 is given in combination with PDR001 at Q2W dose  $d_1$  of LAG525 and Q2W dose  $d_2$  of PDR001. The possibility of synergism or antagonism between the safety profiles of the two drugs is captured in the model of odds of DLT rate with combination doses.

$$\text{LAG525: } \text{logit}(\pi_1(d_1)) = \log(\alpha_1) + \beta_1 \log(d_1/d_1^*)$$

$$\text{PDR001: } \text{logit}(\pi_2(d_2)) = \log(\alpha_2) + \beta_2 \log(d_2/d_2^*)$$

$$\text{Odds}(\pi_{12}(d_1, d_2)) = \pi_{12}(d_1, d_2) / (1 - \pi_{12}(d_1, d_2))$$

$$= \exp(\eta(d_1/d_1^*)(d_2/d_2^*)) (\pi_1(d_1) + \pi_2(d_2) - \pi_1(d_1) \pi_2(d_2)) / ((1 - \pi_1(d_1))(1 - \pi_2(d_2))),$$

where  $\text{logit}(\pi(d)) = \log[\pi(d) / \{1 - \pi(d)\}]$ ,  $d_1^* = 3$  mg/kg and  $d_2^* = 3$  mg/kg are the reference doses of LAG525 and PDR001 respectively,  $\alpha_1, \alpha_2, \beta_1, \beta_2 > 0$  and  $-\infty < \eta < \infty$  is the interaction coefficient.

The Bayesian approach requires the specification of prior distributions for all model parameters. This section provides details of the statistical model, the derivation of prior distributions for the model parameters, and the properties of the adaptive design (dosing recommendations for hypothetical data scenarios and operating characteristics).

### 14.3.1.1 Prior specifications for single agent model parameters

#### Prior for PDR001 parameters ( $\log(\alpha_2)$ , $\log(\beta_2)$ ):

Because more clinical data are available on the class of anti-PD-1 antibody than the anti-LAG-3 antibody, we first derive the prior for single-agent PDR001. This prior will be checked based upon the available single agent data of PDR from CPDR001X2101 study.

This study uses a mixture prior consisting of two components, as specified in Table 14-7. Component 1 is the distribution derived based on PDR001 preclinical data and clinical data on Nivolumab and Pembrolizumab, and is also the component that reflects the low toxicity profile. The assigned weight for component 1 is 80%. Component 2 allows for a case assuming higher toxicity. The assigned weight for component 2 is 20%.

**Table 14-7 Prior distribution of model parameters – phase I single agent PDR001**

Parameter	Means	Standard deviations	Correlation	Weight
Component 1: priors for a low toxicity profile				
$\log(\alpha_2)$ , $\log(\beta_2)$	-2.692, -1.26	1.0, 1.0	0	0.8
Component 2: priors for a more toxicity sensitive population				
$\log(\alpha_2)$ , $\log(\beta_2)$	-2.3, 0	2, 1	0	0.2

#### Component 1:

For the intercept parameter  $\log(\alpha_2)$ , the prior mean of -2.692 is derived based on the a-priori median of an assumed 6.3% DLT rate at the reference dose  $d_2^* = 3$  mg/kg. By setting the standard deviation of  $\log(\alpha_2) = 1$ , the respective upper bound of the 95% a-priori interval of the DLT rate at dose 3 mg/kg is 32.5%, lower than 33%, which represents the a-priori assumption that 3 mg/kg of PDR001 is a safe dose.

For the log-slope parameter  $\log(\beta_2)$ , the prior mean of -1.26 and prior standard deviation of 1 have the following interpretation: when tripling the dose, the odds of having a DLT are multiplied by a factor of  $3^\beta$ , i.e., by 1.4 for the median and approximately (1.0, 9.1) for the 95% interval. This reflects the a-priori assumption that the dose-DLT curve may be quite flat for the anti-PD1 antibody.

#### Component 2:

This weakly informative bivariate normal prior allows for a case with higher toxicity.

For the intercept parameter  $\log(\alpha_2)$ , the prior mean of -2.3 is derived based on the a-priori median of an assumed 9.1% DLT rate at the reference dose  $d_2^* = 3$  mg/kg. By setting the standard deviation = 2, the respective 95% a-priori interval at dose 3 mg/kg is wide (0.2%, 84%), which represents weak prior information.

For the log-slope parameter  $\log(\beta_2)$ , the prior mean of 0 and prior standard deviation of 1 allow for very flat to very steep slopes. Therefore, it is a weakly informative prior. The interpretation is as follows: when tripling the dose, the odds of having a DLT are multiplied by a factor of  $3^\beta$ , i.e., by 3 for the median and (1.2, 2439.2) for the 95% interval.

For both components, the correlation between  $\log(\alpha_2)$  and  $\log(\beta_2)$  is set to 0.

**Prior for LAG525 parameters ( $\log(\alpha_1)$ ,  $\log(\beta_1)$ ):**

Before observing any clinical data, the DLT profile of single-agent LAG525 is expected to be similar to that of single-agent PDR001. Therefore, it is reasonable to use the same mixture prior defined in [Table 14-7](#) for ( $\log(\alpha_1)$ ,  $\log(\beta_1)$ ).

[Table 14-8](#), [Table 14-9](#) and [Table 14-10](#) summarize the DLT rates of the associated prior distribution. The doses not meeting the overdose criteria are bold in the table, i.e. it is not eligible at the start of the study (under the prior).

**Table 14-8 Summary of prior distribution of DLT rates – phase I single agent LAG525 (derived from the mixture prior in Table 14-7)**

LAG525 dose (mg/kg Q2W)	Prior probabilities that Pr(DLT) is in interval:					Quantiles		
	[0, 0.16)	[0.16,0.33)	[0.33, 1]	Mean	SD	2.50%	50.00%	97.50%
0.3	0.939	0.047	0.014	0.049	0.076	0	0.024	0.252
1 (starting dose)	0.9	0.075	0.026	0.069	0.095	0.001	0.039	0.334
3	0.805	0.134	0.061	0.11	0.133	0.006	0.066	0.518
10	0.615	0.2	0.185	0.205	0.233	0.012	0.114	0.946

**Table 14-9 Summary of prior distribution of DLT rates – phase I single agent LAG525 (derived from the Component 1 prior in Table 14-7)**

LAG525 dose (mg/kg Q2W)	Prior probabilities that Pr(DLT) is in interval:					Quantiles		
	[0, 0.16)	[0.16,0.33)	[0.33, 1]	Mean	SD	2.50%	50.00%	97.50%
0.3	0.948	0.046	0.006	0.048	0.059	0	0.028	0.216
1 (starting dose)	0.918	0.071	0.011	0.064	0.069	0.004	0.041	0.257
3	0.849	0.127	0.024	0.09	0.084	0.009	0.064	0.327
10	0.683	0.211	0.106	0.151	0.154	0.013	0.1	0.603

**Table 14-10 Summary of prior distribution of DLT rates – phase I single agent LAG525 (derived from the Component 2 prior in Table 14-7)**

LAG525 dose (mg/kg Q2W)	Prior probabilities that Pr(DLT) is in interval:					Quantiles		
	[0, 0.16)	[0.16,0.33)	[0.33, 1]	Mean	SD	2.50%	50.00%	97.50%
0.3	0.898	0.053	0.048	0.056	0.129	0	0.006	0.496
1 (starting dose)	0.821	0.09	0.089	0.095	0.167	0	0.022	0.653
3	0.624	0.162	0.214	0.193	0.231	0.002	0.092	0.838
10	0.345	0.154	0.501	0.42	0.346	0.006	0.332	0.999

Note: bold values indicate doses not meeting the overdose criterion (less than 25% chance of excessive toxicity) with the prior information only.

To check the performance of the model, the document summarizes some hypothetical dose escalation scenarios. Details regarding dose recommendation are described in [Section 10.4.2](#) of the protocol.

### 14.3.1.2 Hypothetical dose escalation scenarios for the single-agent LAG525 arm

In order to show how the Bayesian model performs, different hypothetical dose escalation scenarios were investigated. The design should make reasonable dose-recommendations during the clinical trial based on the observed DLTs for hypothetical dose escalation scenarios. During the study, the decision to dose escalate after completion of a given cohort and the actual dose chosen for the subsequent cohort will depend on the recommendation of the BLRM per EWOC principle, estimated/predicted exposure at each dose level, and medical review of available clinical and laboratory data.

Some hypothetical dose escalation scenarios to illustrate the dose escalation up to the fourth dose cohort are listed in [Table 14-11](#). The maximum dose increment allowed in the scenarios did not exceed 334% as per escalation rules defined in [Section 6.2.3](#). The recommended next dose level satisfied the EWOC principle.

**Table 14-11 Hypothetical dose escalation scenarios for on-study decisions – phase I single agent LAG525**

Scenario	LAG525 Dose level (mg/kg)	Np at	Ntox	Next Dose Level (NDL)	P(Target) ND	P(Over) ND	Median DLT rate (NDL)
1	1	4	0	3	0.101	0.026	0.054
2	1	4	1	3	0.264	0.108	0.121
3	1	4	2	1	0.365	0.221	0.19
4	1 3	4 3	0 0	10	0.146	0.108	0.079
5	1 3	4 3	0 1	3	0.215	0.055	0.098
6	1 3	4 3	0 2	1	0.21	0.036	0.089
7	1 3	4 6	0 0	10	0.126	0.084	0.068
8	1 3	4 6	0 1	10	0.241	0.193	0.137
9	1 3	4 6	0 2	3	0.338	0.089	0.142

Scenario	LAG525 Dose level (mg/kg)	Np at	Ntox	Next Dose Level (NDL)	P(Target) NDL	P(Over) NDL	Median DLT rate (NDL)
10	1	4	0	10	0.241	0.193	0.137
	3	3	1				
	3	3	0				
11	1	4	0	3	0.338	0.089	0.142
	3	3	1				
	3	3	1				
12	1	4	0	1	0.254	0.034	0.103
	3	3	1				
	3	3	2				
13	1	4	0	3	0.337	0.248	0.191
	3	3	2				
	1	3	0				
14	1	4	0	1	0.367	0.064	0.143
	3	3	2				
	1	3	1				
15	1	4	0	1	0.506	0.212	0.222
	3	3	2				
	1	3	2				
16	1	4	1	10	0.274	0.118	0.128
	3	3	0				
17	1	4	1	3	0.38	0.15	0.168
	3	3	1				
18	1	4	1	1	0.416	0.179	0.192
	3	3	2				
19	1	4	1	10	0.364	0.137	0.16
	3	3	1				
	3	5	0				

Scenario	LAG525 Dose level (mg/kg)	Np at	Nt ox	Next Dose Level (NDL)	P(Target) NDL	P(Over) NDL	Median DLT rate (NDL)
20	1	4	1	3	0.463	0.102	0.175
	3	3	1				
	3	5	1				
21	1	4	1	1	0.445	0.082	0.166
	3	3	1				
	3	5	2				
22	1	3	0	3	0.479	0.182	0.201
	3	5	2				
	1	3	1				
23	1	3	0	3	0.429	0.128	0.173
	3	5	2				
	1	3	1				
	1	4	0				

Overall, the model is showing appropriate behaviors, in agreement with clinical sense and decision making process. The dose levels investigated correspond to the provisional dose levels specified in [Section 6.2.2](#).

#### 14.3.1.3 Prior specifications for LAG525 + PDR001 combination model parameters

The 5-parameter BLRM used to guide the dose escalation for the combination of LAG525+PDR001 will use DLT information from both dose escalation arms: patients receiving the single-agent LAG525 and patients receiving the LAG525+PDR001 combo. At each dose escalation meeting, data from the last completed single agent cohort will be incorporated directly into the model, without down-weighting. The available single agent data from CPDR001X2101 study will also be used to check the prior information for the BLRM model.

The prior distributions of model parameters for single-agent LAG525 and single-agent PDR001 have been derived in [Section 14.3.1.1](#).

#### Prior for the interaction parameter $\eta_{12}$ :

A normal prior distribution for the interaction parameter  $\eta_{12}$  is to be derived to reflect the current uncertainty about the toxicity profile of the combination of LAG525 and PDR001. The risk of significant positive interaction between LAG525 and PDR001 cannot be totally excluded. The interaction parameter  $\eta_{12}$  was chosen accordingly but with a degree of uncertainty in order to allow for the possibility that the interaction may be positive or negative. Therefore the following assumption is made for the interaction parameter:

- $\eta_{12}$  is normally distributed and centered at  $\log(1.5) \cdot (d_1/d_1^*) \cdot (d_2/d_2^*)$ , i.e. 50% increase in odds of DLT due to interaction compared to independence at the anticipated combination reference dose  $d_1^*$  and  $d_2^*$ .
- 97.5th percentile of  $\eta_{12}$  is  $\log(5) \cdot (d_1/d_1^*) \cdot (d_2/d_2^*)$ , i.e. 5-fold increase in odds of DLT due to interaction compared to independence at the combination reference dose  $d_1^*$  and  $d_2^*$ .

Therefore the prior mean for  $\eta_{12}$  is 0.405 and the prior standard deviation is 0.614. This allows for the potential of both synergism and antagonism between the safety profiles of the two drugs. Since the interaction is dose-dependent (see model definition in [Section 10.4.2](#)), the prior for the interaction parameter has a simple interpretation only at the anticipated combination reference dose of LAG525 = 3 mg/kg Q2W and PDR001 = 3 mg/kg Q2W.

[Table 14-12](#) summarizes the prior distributions of the model parameters and [Table 14-13](#) summarizes the corresponding prior distribution for the DLT rates at each provisional dose level.

**Table 14-12 Prior distribution of model parameters – phase I LAG525 + PDR001**

Parameters	Description	Means	Standard deviations	Correlation	Weight
log( $\alpha_1$ ), log( $\beta_1$ )	LAG525 parameters	-2.692, -1.26	1.0, 1.0	0	0.8
		-2.3, 0	2, 1	0	0.2
log( $\alpha_2$ ), log( $\beta_2$ )	PDR001 parameters	-2.692, -1.26	1.0, 1.0	0	0.8
		-2.3, 0	2, 1	0	0.2
$\eta_{12}$	Interaction LAG525-PDR001	0.405	0.614		

**Table 14-13 Summary of prior distribution of DLT rates – phase I LAG525 + PDR001**

LAG525 dose (mg/kg Q2W)	Prior probabilities that Pr(DLT) is in interval:					Quantiles		
	[0, 0.16)	[0.16, 0.33)	[0.33, 1]	Mean	SD	2.50%	50.00%	97.50%
PDR001 = 0.3 mg/kg Q2W								
0.3	0.834	0.129	0.037	0.097	0.105	0.004	0.066	0.386
1	0.778	0.168	0.053	0.117	0.119	0.009	0.082	0.451
3	0.658	0.241	0.102	0.16	0.148	0.019	0.114	0.61
10	0.448	0.292	0.261	0.264	0.238	0.029	0.181	0.96
PDR001 = 1 mg/kg Q2W								
0.3	0.778	0.169	0.053	0.117	0.118	0.009	0.083	0.448
1	0.709	0.216	0.075	0.14	0.13	0.015	0.102	0.509
3	0.556	0.3	0.144	0.191	0.161	0.026	0.143	0.673
10	0.309	0.288	0.403	0.339	0.259	0.033	0.264	0.975
PDR001 = 3 mg/kg Q2W								
0.3	0.655	0.243	0.102	0.16	0.147	0.019	0.116	0.599
1	0.551	0.303	0.146	0.192	0.161	0.026	0.144	0.663
3	0.35	0.329	0.321	0.282	0.208	0.035	0.226	0.831
10	0.211	0.135	0.654	0.534	0.339	0.013	0.556	0.997

LAG525 dose (mg/kg Q2W)	Prior probabilities that Pr(DLT) is in interval:			Mean	SD	Quantiles		
	[0, 0.16)	[0.16,0.33)	[0.33, 1]			2.50%	50.00%	97.50%
PDR001 = 10 mg/kg Q2W								
0.3	0.438	0.298	0.263	0.266	0.236	0.029	0.184	0.957
1	0.302	0.287	0.411	0.341	0.258	0.033	0.268	0.972
3	0.208	0.137	0.655	0.535	0.339	0.013	0.561	0.997
10	0.21	0.04	0.75	0.71	0.398	0	0.981	1

Note: bold values indicate doses not meeting the overdose criterion (more than 25% chance of excessive toxicity) with the prior information only.

#### 14.3.1.4 Hypothetical dose escalation scenarios for LAG525 + PDR001 combination arm

Table 14-14 shows on-study dosing recommendations for some hypothetical data scenarios.

Note that the next dose combination is selected in concordance with the provisional dose levels specified in Section 6.2.2 of the protocol wherever it is allowed, to mimic possible on-study escalation steps.

**Table 14-14 Hypothetical dose escalation scenarios for on-study decisions – phase I LAG525 + PDR001**

Scenario	Dose combination LAG525 (mg/kg Q2W) / PDR001 (mg/kg Q2W)	Npat	Ntox	Next dose combination (NDC)	P(target) NDC	P(over) NDC	Median DLT rate (NDC)
1	1/1	4	0	1/3	0.237	0.052	0.108
2	1/1	4	1	1/3	0.408	0.163	0.181
3	1/1	4	2	0.3/1	0.409	0.183	0.187
4*	1/0 (single agent cohort 1) 1/1	3 4	0 2	1/1	0.444	0.183	0.195
5	1/1 1/3	4 3	0 0	3/3	0.32	0.129	0.144
6	1/1 1/3	4 3	0 1	1/3	0.364	0.082	0.148
7	1/1 1/3	4 3	0 2	1/1	0.358	0.064	0.141
8	1/1 1/3	4 5	1 0	3/3	0.395	0.191	0.187
9	1/1 1/3	4 5	1 1	1/3	0.481	0.104	0.18

Scenario	Dose combination LAG525 (mg/kg Q2W) / PDR001 (mg/kg Q2W)	Npat	Ntox	Next dose combination (NDC)	P(target) NDC	P(over) NDC	Median DLT rate (NDC)
10	1/1 1/3	4 5	1 2	1/1	0.486	0.113	0.184
11	1/1 0.3/1	4 3	2 0	1/1	0.441	0.128	0.177
12	1/1 0.3/1	4 3	2 1	0.3/1	0.489	0.223	0.222
13	1/1 0.3/1	4 3	2 2	Stop			
14*	1/0 (single agent cohort 1) 1/1 0.3/1	3 4 3	0 2 2	0.3/0.3	0.495	0.241	0.231
15*	1/0 (single agent cohort 1) 3/0 (single agent cohort 2) 1/1 1/3	3 3 4 3	0 0 0 0	3/3	0.293	0.088	0.127
16*	1/0 (single agent cohort 1) 3/0 (single agent cohort 2) 1/1 1/3	3 3 4 3	0 0 0 1	3/3	0.4	0.235	0.205
17*	1/0 (single agent cohort 1) 3/0 (single agent cohort 2) 1/1 1/3	3 3 4 3	0 0 0 2	1/1	0.276	0.032	0.117
18*	1/0 (single agent cohort 1) 3/0 (single agent cohort 2) 1/1 1/3	3 3 4 3	0 1 1 1	1/3	0.526	0.189	0.217
19*	1/0 (single agent cohort 1) 3/0 (single agent cohort 2) 1/1 1/3	3 3 4 3	0 1 1 2	1/1	0.543	0.173	0.214

Scenario	Dose combination LAG525 (mg/kg Q2W) / PDR001 (mg/kg Q2W)	Npat	Ntox	Next dose combination (NDC)	P(target) NDC	P(over) NDC	Median DLT rate (NDC)
20*	1/0 (single agent cohort 1) 3/0 (single agent cohort 2) 1/1 1/3	3 3 4 3	0 0 1 1	1/3	0.466	0.15	0.188

Scenario	Dose combination LAG525 (mg/kg Q2W) / PDR001 (mg/kg Q2W)	Npat	Ntox	Next dose combination (NDC)	P(target) NDC	P(over) NDC	Median DLT rate (NDC)
21*	1/0 (single agent cohort 1) 3/0 (single agent cohort 2) 1/1 1/3	3 3 4 3	0 0 1 2	1/1	0.47	0.13	0.186

\*PDR001 dose of 0 represents a single-agent LAG525 cohort. Data from patients receiving the single-agent LAG525 are incorporated directly into the model, without down-weighting

Within Table 14-14, P(Target) NDC represents the probability that the true DLT rate for the dose lies in the target interval (16%, 33%) while P(Over) NDC represents the probability that the true DLT rate for the dose exceeds 33%.

Within Table 14-14, it can be seen that the model generally leads to decisions that are in agreement with clinical sense. The dose levels investigated correspond to the provisional dose levels specified in Section 6.2.2.

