Dose escalation decisions will be made by investigators and Novartis study personnel. For each arm, decisions will be based on a synthesis of all relevant data available from all dose levels evaluated in the ongoing study including safety information, DLTs, all CTCAE Grade  $\geq 2$  toxicity data during Cycle 1 (arm A and Arm C), and cycles 1 and 2 (arm B), PK, [REDACTED] data from evaluable patients. The recommended dose for the next cohort of subjects will be guided by the BLRM with EWOC principle ([Section 2.2](#)) and determined by a synthesis of all available data from the cohort.

The adaptive Bayesian methodology provides an estimate of all dose levels of LAG525 and PDR001 that do not exceed the MTD and incorporates all DLT information at all dose levels for this estimation. In general, the next dose will have the highest chance that the DLT rate will fall in the target interval [16-33%) and will always satisfy the EWOC principle. In all cases, the dose for the next cohort will not exceed a 333% ( $1/2 \text{ Log}_{10}$ ) increase from the previous dose. Smaller increases in dose may be recommended by the Investigators and Sponsor upon consideration of all of the available clinical data.

If the first 2 patients in a previously untested dose level experience a DLT, further enrollment to that cohort will stop and the BLRM will be updated with this new information. Re-evaluation of the available safety, PK, [REDACTED] data will occur. By incorporating information gained at the preceding dose levels, additional patients may be enrolled at this dose level or a lower dose level as agreed by Investigators and Novartis personnel and if the BLRM predicts that the risk that this dose exceeds the MTD remains below 25% (EWOC).

Dose escalation for each arm (Arm A and Arm C, single-agent LAG525 or Arm B, combination of LAG525 and PDR001) will continue until identification of the RP2D or the MTD of the single-agent or combination.

The MTD/RP2D will be determined if the following conditions are met:

1. at least 6 patients have been treated at this dose
2. this dose satisfies one of the following conditions:
  - a. the posterior probability of targeted toxicity at this dose exceeds 50%, or
  - b. minimum of 21 patients for the single agent Arm A or 15 patients for the combination Arm B, or 12 patients for the Japanese dose escalation Arm C have already been treated on the trial for this arm.

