$$\text{PDR001: } \text{logit}(\pi_2(d_2)) = \log(\alpha_2) + \beta_2 \log(d_2/d_2^*)$$

$$\text{Odds}(\pi_{12}(d_1, d_2)) = \pi_{12}(d_1, d_2) / (1 - \pi_{12}(d_1, d_2))$$

$$= \exp(\eta(d_1/d_1^*)(d_2/d_2^*)) (\pi_1(d_1) + \pi_2(d_2) - \pi_1(d_1)\pi_2(d_2)) / ((1 - \pi_1(d_1))(1 - \pi_2(d_2))),$$

where  $\text{logit}(\pi(d)) = \log[\pi(d) / \{1 - \pi(d)\}]$ ,  $d_1^* = 3 \text{ mg/kg}$  and  $d_2^* = 3 \text{ mg/kg}$  are the reference doses of LAG525 and PDR001 respectively,  $\alpha_1, \alpha_2, \beta_1, \beta_2 > 0$  and  $-\infty < \eta < \infty$  is the interaction coefficient.

At the time of each LAG525+PDR001 dose escalation analysis, DLT data up to, and including, the last completed cohort from the single agent dose escalation will be included in the LAG525+PDR001 BLRM. Single agent LAG525 data will be incorporated directly into the BLRM since this data comes from the same study. Single agent PDR001 data from study PDR001X2101 dose escalation will also be utilized. In order to account for between study variability, the DLT data obtained from PDR001X2101 will be discounted (e.g. using down-weighting approach).

The Bayesian approach requires the specification of prior distributions for the model parameters. The prior distributions for the BLRM are derived based on available pre-clinical data on LAG525 and PDR001 and also clinical data for nivolumab and pembrolizumab. For further details on the BLRM model including the prior specification for the model parameters, and examples of hypothetical decisions that may be followed during the dose escalation, refer to [Appendix 14.3.1](#).

After each cohort of patients, the posterior distributions for the probabilities of DLT rates at different dose levels (or combinations) are obtained. Dose recommendation will be based on posterior summaries including the mean, median, standard deviation, 95%-credible interval, and the probability that the true DLT rate for each dose lies in one of the following categories:

- [0,16%] under-dosing
- [16%,33%] targeted toxicity
- [33%,100%] excessive toxicity

Dose recommendation will also be guided by the EWOC principle, which mandates the dose for the next cohort to have less than 25% chance of excessive toxicity. The final estimate of the MTD(s)/ RP2D(s) will also satisfy this condition.

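### Table 14-14, scenario 14 prints P(over) 0.241 for 0.3/0.3 mg/kg, but the model as written gives about 0.270, above the 25% EWOC limit

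*Protocol*

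**What the plan says.** Section 10.4.2 of the protocol states that the EWOC principle "mandates the dose for the next cohort to have less than 25% chance of excessive toxicity", where excessive toxicity means a true DLT rate of 33% or more. Section 6.2.3 adds that the next dose "will always satisfy the EWOC principle".

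The note under Table 14-14 defines the column at issue: "P(Over) NDC represents the probability that the true DLT rate for the dose exceeds 33" per cent. Scenario 14 of Table 14-14 reads "1/0 (single agent cohort 1) 1/1 0.3/1 3 4 3 0 2 2 0.3/0.3 0.495 0.241 0.231". That is: 0 DLTs in 3 patients on LAG525 1 mg/kg alone, 2 in 4 at 1/1, 2 in 3 at 0.3/1, and next combination 0.3/0.3 with P(target) 0.495, P(over) 0.241 and median 0.231. Scenario 13 has the same combination data without the single-agent cohort, and its entry is Stop.

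A footnote covers the starred rows, of which scenario 14 is one: "Data from patients receiving the single-agent LAG525 are incorporated directly into the model, without down-weighting". On zero doses, Appendix 14.3.1 says of the single-agent model: "Note that for a dose equal to zero, the probability of toxicity is zero". The text after the table concludes that "it can be seen that the model generally leads to decisions that are in agreement with clinical sense".

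**The concern.** Scenarios 13 and 14 together say that three DLT-free patients on LAG525 alone are enough to turn a stop into an eligible combination. The printed margin is thin: 0.25 − 0.241 = 0.009. The protocol specifies model, priors and data fully, so the figure can be checked without outside information.

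At stake is whether the table describes the written model correctly in the rows where single-agent data enter the combination fit. Section 10.4.2 and SAP 2.6.1 both plan to use single-agent LAG525 data in that way.

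**Working it through.** **Inputs**

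- Model: Appendix 14.3.1; 3 mg/kg and 3 mg/kg "are the reference doses of LAG525 and PDR001 respectively".
- Priors (Table 14-12), for each drug: weight 0.8 on log α ~ N(mean −2.692, SD 1), log β ~ N(−1.26, 1); weight 0.2 on log α ~ N(−2.3, 2), log β ~ N(0, 1); correlation 0. Interaction η ~ N(0.405, SD 0.614).
- Data: scenario 14 as quoted above.

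**Formulas**

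Write the single-drug odds as o_i(d) = α_i (d/3)^β_i. The protocol's combination odds reduce to

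odds12 = exp[η (d1/3)(d2/3)] × (o1 + o2 + o1·o2).

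The multiplier on η is 1/9 at 1/1, 1/30 at 0.3/1 and 0.01 at 0.3/0.3. At PDR001 dose 0, o2 = 0 and the interaction term is 1, so the DLT rate is that of LAG525 alone. The likelihood is

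L = [1 − π(1,0)]³ × π(1,1)² [1 − π(1,1)]² × π(0.3,1)² [1 − π(0.3,1)].

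P(over) is the L-weighted share of prior draws with π(0.3,0.3) ≥ 0.33.

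**Step 1: does the refit reproduce the protocol elsewhere?** Three prior rows of Table 14-13 were checked and match within 0.002. The unstarred rows of Table 14-14 agree within about 0.01; for example, scenario 3 gives 0.189 (printed 0.183), scenario 10 gives 0.113 (0.113) and scenario 12 gives 0.218 (0.223). Scenario 13 gives 0.343 at 0.3/0.3, consistent with its Stop entry.

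**Step 2: scenario 14.** Repeated sampling runs with different seeds and separately written code give P(over) 0.270 to 0.272, P(target) about 0.480 and median 0.239. A coarse quadrature gives 0.275. The Monte Carlo standard error is 0.0003 in the largest runs (20 million draws) and below 0.001 in the others. The gap is 0.270 − 0.241 = 0.029, so simulation noise in the refit does not explain it. In the same fit, 0.3/1 has P(over) 0.448 and 1/1 has 0.520.

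**Step 3: could a small slip in the inputs explain it?** P(over) at 0.3/0.3 under variants:

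| Variant | P(over) |
|---|---|
| Single-agent n of 4 or 6 instead of 3 | 0.266, 0.265 |
| Added single-agent cohort at 3 mg/kg | 0.266 |
| Cut-off 1/3 instead of 0.33 | 0.264 |
| Same mixture component for both drugs | 0.263 |
| Interaction mean 0 | 0.279 |
| Component 1 weight 0.9 | 0.238, but scenario 3 then gives 0.155 (printed 0.183) and scenario 12 gives 0.185 (0.223) |
| Mixture weights held at prior values | 0.242, but this is not a Bayesian update |

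**Step 4: the starred rows together.** P(over) as printed, with PDR001 dose exactly 0, and with the zero coded as 10⁻⁶ mg/kg:

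| Scenario | Printed | Exact 0 | 10⁻⁶ |
|---|---|---|---|
| 4 | 0.183 | 0.2008 | 0.1900 |
| 14 | 0.241 | 0.2703 | 0.2441 |
| 15 | 0.088 | 0.0925 | 0.0908 |
| 16 | 0.235 | 0.2398 | 0.2370 |
| 17 | 0.032 | 0.0373 | 0.0326 |
| 18 | 0.189 | 0.1880 | 0.1850 |
| 19 | 0.173 | 0.1802 | 0.1790 |
| 20 | 0.150 | 0.1545 | 0.1489 |
| 21 | 0.130 | 0.1471 | 0.1319 |

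With an exact zero, scenarios 4, 14 and 21 miss by more than 0.01, and only scenario 14 crosses 0.25. With 10⁻⁶, all nine rows lie within 0.007 of print. For scenario 14, 10⁻⁸ gives 0.252 and 10⁻⁵ gives 0.238.

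**Step 5: why a tiny dose would matter.** The PDR001 slope prior allows very flat curves. At the lower 2.5% point of component 1, β = exp(−1.26 − 1.96) = 0.040, and (10⁻⁶/3)^0.040 = exp(−14.91 × 0.040) ≈ 0.55. Over half the reference-dose odds would then be charged to patients who received no PDR001, and their lack of DLTs would pull the estimated PDR001 risk down.

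**The case against.** The strongest reply accepts the number and disputes its weight.

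- Scenario 14 has only a 1 mg/kg single-agent cohort, whereas Sections 4.1 and 6.2.3 start the combination after a 3 mg/kg cohort is complete. The row could not arise as written. This stands as a limit on consequence; adding such a cohort, as in the variants above, leaves P(over) above 25%.
- Section 10.4.2 also brings in discounted PDR001X2101 data. Section 1.2.2.2 reports 58 patients there with no DLT at its cut-off. Table 14-14 contains none of this, so it is not the complete on-study model. This stands.
- The table is not the only evidence on model behaviour. Appendix 14.3.1.5 reports simulated operating characteristics (five scenarios, 1000 trials each), which this check does not touch. Dose decisions also draw on all clinical data. This stands.
- Escalation appears finished: the study status entries of Amendments 09 and 10 both give 255 patients treated in that part. This stands, and it makes the point retrospective.

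A reader might infer that P(over) is understated throughout, since 18 of the 20 printed values lie below the refit. Most of those gaps are trivial, and scenarios 12 and 18 go the other way. A reader might also infer that the program used on study was permissive. The documents do not show that program, and the zero-dose explanation is only an inference from the pattern of gaps.

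**Conclusion.** Scenario 14 does not follow from the model as written. Its P(over) is about 0.270, not 0.241, and the printed row shows as EWOC-eligible a combination that the written model places above the 25% limit. The result rests on the Table 14-12 priors, the printed counts, full weight for the single-agent cohort and a PDR001 dose of exactly zero, all of which the protocol states.

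The larger gaps are confined to rows with single-agent data. They fit a zero dose coded as a small positive number, which would contradict the protocol's zero-dose statement, but the documents do not confirm this cause.

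It is tempting to say that the table turns a stopping situation into continued dosing. The documents do not support that. The row is hypothetical, and although 0.3/0.3 is the lowest combination listed in Table 6-3, the footnote there allows additional and intermediate levels. The supportable statement is that the scenario 14 entry and the EWOC rule must be reconciled. No actual dosing decision is shown to be wrong, and no dose or clinical rule is proposed here.

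**What to change.** 1. Rerun the nine starred rows of Table 14-14 (scenarios 4 and 14 to 21) with the PDR001 dose set to exactly zero for single-agent cohorts, and correct the printed P(target), P(over) and medians. Longer chains alone would not cure a dose-coding problem, and editing scenario 14 alone would leave scenarios 4 and 21 uncorrected.
2. Reconcile the next-combination entry of scenario 14 with Sections 10.4.2 and 6.2.3.
3. Confirm in the analysis documentation that the program behind the MTD/RP2D estimate reported under SAP 2.6.1 treats single-agent cohorts as the protocol states. If it does not, report the refitted estimates.

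The table work is a few hours of computation and a correction to one appendix table. The program check is small unless it finds a difference.
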